4.3.7. Rationale for Primary Efficacy Endpoint and Secondary Endpoints

Powering a study for superiority on the basis of mortality was not considered ethical or feasible due to the large number of subjects that would need to be included. Multiple non-mortality clinical outcomes were considered as potential primary endpoints (such as progression of AdV disease or infection) and were rejected for a variety of reasons, including: (1) lack of consensus definitions of AdV disease and progression; (2) multiple etiologies that can result in similar signs/symptoms, and (3) the reluctance to require invasive diagnostic procedures to document progressive AdV disease (e.g., liver biopsy to document AdV hepatitis). For example, respiratory compromise can be the result of worsening AdV disease, the sequelae of the patient's conditioning regimen, or another infectious etiology; and renal dysfunction can be the culmination of multiple nephrotoxic insults, including AdV disease, and is commonly observed after CDV administration as well other known nephrotoxic medications. Gut injury is perhaps even more complicated with clinical, gross pathology and even histopathologic analysis unable to differentiate from progression of AdV disease, gut GVHD, and injury related to prolonged oral administration of BCV. In contrast, a primary endpoint based on control of AdV viremia is considered to be both feasible and clinically relevant.

The primary efficacy endpoint selected for this study is the time-averaged area under the concentration-time curve (AAUC) for plasma AdV viremia (\log_{10} copies/mL) through Week 16 post-randomization. This viral AAUC endpoint was selected based on evidence collected from prior BCV clinical trials and expanded access programs, as well as data from the literature evaluating SoC, showing that virologic response is predictive of clinical outcomes. AdV viremia has been demonstrated in natural history studies to be a valid predictor of disease-related outcomes, with thresholds of peak viremia identified which predict significant changes in expected survival, thus supporting the use of AdV viremia as a surrogate that is reasonably likely to predict clinical benefit. In addition, the positive impact on survival has been noted with reductions in AdV viral load following investigational interventions, including with adoptive T cells (Feucht 2015), IV CDV, and BCV (see Section 4.3.7.1 and Section 4.3.7.2).

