To illustrate the clinical relevance of this endpoint, Chimerix has analyzed the data from pediatric HCT subjects enrolled in Cohorts A and B in the CMX001-304 study with AdV viral load ≥ 1000 copies/mL at baseline who were within 100 days of transplant ($n = 40$). In this group, 28% (11 of 40) subjects died by Week 16. A boxplot looking at distribution of AAUC through Week 16 by vital status (i.e., alive or dead) at Week 16 shows that survivors had reduced AAUC when compared with non-survivors (t-test $p = 0.11$) (Figure 2).

Figure 2: Study CMX001-304: AAUC through Week 16, Mortality at Week 16

Similar analyses have been conducted for two retrospective patient cohorts: a historical dataset dating back more than 10 years from Royal Manchester Children’s Hospital in the United Kingdom (UK) (the “Manchester Cohort”) (Figure 3) and preliminary data from three countries (France, Spain, and UK) from the AdVance study (Figure 4), which is a natural history study sponsored by Chimerix that will explore the association of AdV viremia, response to SoC therapy, and clinical outcomes (including overall survival and non-relapse mortality) in a contemporary multicenter cohort. The results from these two retrospective patient cohorts also support the correlation between the proposed endpoint (viral AAUC) and mortality under SoC

treatment with IV CDV (Manchester Cohort n = 24, p = 0.0032; AdVance n = 51, p = 0.007). (Note that a Manchester Cohort analysis looking at AAUC vs. mortality was not available in time to contribute; therefore, a previous analysis looking at time-averaged area under the curve minus baseline, or AAUCMB, is presented.)

Figure 3: Manchester Cohort: AAUCMB through Week 16, Mortality at Week 16

[figure not shown]
[figure not shown]

Figure 4: AdVance Study: AAUC through Week 16, Mortality at Week 16 (Preliminary Data from UK, Spain, and France)

A viral AAUC endpoint also provides the opportunity to correlate total viral burden with secondary endpoints of clinical outcomes, including all-cause and non-relapse mortality, as well as other clinical benefits, such as decreased progression to Adv pneumonia, and decreased number of days spent in the hospital or intensive care unit (ICU).

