4.3.7.1. Study CMX001-304

In a landmark analysis of data from Study CMX001-304, lower mortality outcomes were observed among subjects with early virologic response across both Cohort A (localized or asymptomatic AdV infection) and Cohort B (disseminated disease). Specifically, improved survival was observed among pediatric subjects with an undetectable viremia result at Week 4 (mortality 24% Cohort A and 29% Cohort B vs. 44% and 47%, respectively among non-responders who did not achieve undetectable AdV viremia at Week 4) (see Table 4). Pediatric subjects with disseminated disease (Cohort B) who achieved undetectable AdV viremia by Week 6 also had an improved overall survival (25% mortality vs. 54% mortality in pediatric subjects who did not achieve undetectable AdV viremia at Week 6). Similar observations were made in adult subjects, although overall survival rates were lower.

Table 4: Study CMX001-304: Early Virologic Response and Mortality Outcome

Responder Definition	Pediatrics			Adults		
	Proportion Responder ^a	Mortality among Responders	Mortality among Non-responders	Proportion Responder ^a	Mortality among Responders	Mortality among Non-responders
Cohort A (localized or asymptomatic AdV infection)						
Undetectable at Week 4	17/26 (65%)	4/17 (24%)	4/9 (44%)	7/13 (54%)	3/7 (43%)	5/6 (83%)
Undetectable at Week 6	17/25 (68%)	5/17 (29%)	2/8 (25%)	8/13 (62%)	4/8 (50%)	4/5 (80%)
Cohort B (disseminated AdV disease)						
Undetectable at Week 4	24/43 (56%)	7/24 (29%)	9/19 (47%)	9/26 (35%)	5/9 (56%) ^b	15/17 (88%)
Undetectable at Week 6	28/41 (68%)	7/28 (25%) ^b	7/13 (54%)	10/24 (42%)	5/10 (50%) ^b	13/14 (93%)

^a Denominator reflects subjects with baseline AdV viremia still on study at Week 4 or Week 6.

^b $p < 0.05$ vs. non-responders, Cox model for time to death.

Note: Cohort A total n (pediatric n, adult n): Enrolled 65 (42, 23), Week 4: 39 (26, 13), Week 6: 38 (25, 13).

Note: Cohort B total n (pediatric n, adult n): Enrolled 93 (58, 35), Week 4: 69 (43, 26), Week 6: 65 (41, 24).

[figure not shown]

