5.2. Secondary and Exploratory Objectives

5.2.1. Secondary Objectives:

- To assess the incidence of and time to all-cause, non-relapse, and AdV-associated mortality in pediatric subjects treated with BCV vs. SoC
- To assess the correlation between virologic response and clinical outcome
- To describe the incidence of and time to virologic relapse in subjects who have previously achieved undetectable AdV viremia
- To assess resolution or progression in clinical symptoms associated with AdV disease (i.e., resolution of all disease to no disease among subjects with probable or definitive AdV disease at baseline and progression from no disease to any probable or definitive AdV disease among asymptomatic subjects at baseline)
- To assess the correlation between AdV hexon “serotype,” virologic response, and clinical outcome
- To evaluate the emergence of viral resistance among subjects treated with BCV vs. SoC
- To characterize plasma BCV PK profiles and evaluate the impact of covariates of interest on PK
- To characterize the potential impact of plasma BCV exposure on clinical safety, virologic, and mortality endpoints, and to evaluate the modifying influence of various covariates of interest on these relationships and endpoints
- To assess virologic response in other non-plasma biologic compartments (urine, stool, respiratory secretions), as well as the association between detectable AdV viral load in these compartments at AdV viremia clearance with subsequent AdV viremia relapse

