12. STATISTICS

All summaries and analyses will be presented in tabular or graphical form. Statistical methods will be described in detail in the Statistical Analysis Plan (SAP), which will be initially finalized as soon as possible during study enrollment with subsequent amendments clearly documenting changes to the plan throughout the study. No amendments to the SAP will be made after the database lock for the primary analysis and subsequent changes will be presented as post hoc analyses. All statistical analyses will be conducted using SAS[®] software, unless otherwise specified in the SAP.

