12.1. Determination of Sample Size

A total of approximately 141 subjects will be enrolled into this study. Sample size calculations were based on the primary endpoint, i.e., AAUC through Week 16. Assuming the observed standard deviation of 1.03 log₁₀ copies/mL in AAUC at Week 16 from a comparable subset of SoC subjects, the study has > 90% power with the currently planned sample size to demonstrate superiority of BCV vs. SoC, given that the true difference in means is > 0.6 log₁₀ copies/mL (i.e., an effect size of ~ 0.58). In addition, the overall mortality at Week 16 non-inferiority comparison will have > 80% power in the event that the expected mortality for SoC is 20% to 30% and there is a true mortality advantage of 6% to 9% in favor of BCV ([Feghoul 2015](#), [Hiwarkar 2017](#), [Mynarek 2014](#)).

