12.4. Efficacy Analyses

12.4.1. Primary Efficacy Endpoint

The primary AAUC analysis will utilize all randomized subjects (ITT) in an analysis of covariance (ANCOVA) with all stratification factors included in the model: T cell-depletion method (alemtuzumab or ex vivo cell selection vs. ATG), time from HCT to randomization (< 28 days vs. \geq 28 days), and baseline AdV viremia (continuous \log_{10} copies/mL). These stratification factors have been selected as those that are clearly related to time to immune reconstitution (time from HCT to confirmed AdV viremia > 1000 copies/mL and thus randomization, procedural differences in depth and duration of immune suppression by T cell-depletion method) with resulting expected differences in clearance of viremia, and/or association with mortality (peak viral load). Regarding baseline AdV viremia, subjects will be stratified at the time of randomization according to \geq 10,000 vs. < 10,000 copies/mL; however, this factor will be included in the analysis as a continuous covariate in order to improve power in determining a treatment effect. In the ANCOVA, AdV viremia values that are undetectable will be imputed at 99 copies/mL (i.e., one less than the lower limit of detection of 100 copies/mL) and values that are detected, but not quantifiable (BLQ) will be imputed at 189 copies/mL (i.e., one less than the lower limit of quantification of 190 copies/mL).

Subjects who die or are lost to follow-up (i.e., drop-outs) prior to Week 16 are accounted for inherently in the AAUC approach by truncating their follow-up period, thereby normalizing AUC over time of follow-up (Li 2012). It should be noted that subjects lost to follow-up are anticipated to be zero or negligible, and approximately 16% to 24% of subjects are expected to die by Week 16. Regardless, the primary analysis will be supplemented by a number of planned sensitivity analyses to assess the impact of subjects who die prior to Week 16 and other potential influential elements on the primary inference and to allow for a more comprehensive assessment of efficacy.

The first three approaches are proposed to account for these subjects in a typical missing data framework:

- Jump to reference imputation, where the missing part of the trajectory is imputed from the control group average ([Kenward 2015](#)).

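### Does cutting AAUC off at death spoil the planned correlation between virologic response and mortality?

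*Combined protocol and SAP*

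**What the plan says.** Section 5.2.1 lists a secondary objective: "To assess the correlation between virologic response and clinical outcome". It names no virologic measure and no model. Section 4.3.7 adds that AAUC "provides the opportunity to correlate total viral burden with secondary endpoints of clinical outcomes, including all-cause and non-relapse mortality".

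For this trial, Section 12.4.1 handles death by stopping the curve: such subjects are "accounted for inherently in the AAUC approach by truncating their follow-up period, thereby normalizing AUC over time of follow-up". The sensitivity analyses for deaths that follow there concern the comparison of brincidofovir (BCV) with standard of care (SoC). Section 12.4.2 also covers treatment comparisons, and Section 12.7 relates plasma drug exposure, not viremia, to mortality. Section 12 leaves detailed methods to an SAP, which can be amended until the database lock for the primary analysis. That SAP is not in the supplied text.

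On other data the protocol shows three ways of linking virus to death:

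- Section 4.3.7 shows the "distribution of AAUC through Week 16 by vital status (i.e., alive or dead) at Week 16" in 40 pediatric subjects of Study CMX001-304, 11 of whom died (t-test p = 0.11). It does not say how that AAUC treated death.
- Section 4.3.7.1 gives a landmark analysis. The footnote to Table 4 reads "Denominator reflects subjects with baseline AdV viremia still on study at Week 4 or Week 6".
- Section 4.3.7.2 describes a Cox model with viral load as a time-varying covariate.

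**The concern.** An average of log10 viremia that ends at death is taken over a different window from a survivor's average. Section 4.4 describes viremia that clears over weeks. A subject who dies in Week 5 is then averaged over the high part of the curve only, while a survivor also contributes many low weeks. Comparing the two groups would show higher AAUC in those who died even if the virus had nothing to do with the deaths.

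The method is left open, and one of the sponsor's own displays is of this type. Section 4.3.7 leans on the virus-survival link as "supporting the use of AdV viremia as a surrogate that is reasonably likely to predict clinical benefit". The worry is that this trial could report a correlation produced partly by the timing of deaths and cite it in support of the surrogate.

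**Working it through.** **The plan's own figure.** Section 12.1 claims more than 90% power, "Assuming the observed standard deviation of 1.03" log10 and a difference of 0.6, with 94 and 47 subjects. The effect size is 0.6/1.03 = 0.5825 and the standard error factor is √(1/94 + 1/47) = 0.1787. So z = 0.5825/0.1787 − 1.96 = 1.30, which gives 90.3% (89.9% with the noncentral t). The claim reproduces to rounding.

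**Expected deaths.** Sections 12.1 and 12.4.1 agree. With SoC mortality 20% and BCV 14%, (47 × 0.20 + 94 × 0.14)/141 = 16%. With 30% and 21%, the same sum gives 24%. That is 23 to 34 deaths.

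**Direction.** The floor is log10(99) = 1.996 (Section 12.4.1). Take a subject at 4.0 who falls linearly to the floor in 4 weeks; the area over those weeks is 4 × (4 + 1.996)/2 = 11.99.

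- Survivor: (11.99 + 12 × 1.996)/16 = 2.25.
- Death at Week 4: 11.99/4 = 3.00, an excess of 0.75.
- Death at Week 8: (11.99 + 4 × 1.996)/8 = 2.50, an excess of 0.25.

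For any curve that never rises, the average to an earlier stop is at least the average to Week 16. With a flat curve the excess is zero. With viremia rising in everyone it is negative.

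**Size.** I simulated 141 subjects with weekly samples and death unrelated to virus. Mortality was 16% or 24% in both arms, AAUC ran to the last sample before death, and a t-test compared groups by Week 16 vital status (1,500 datasets per cell). From Section 4.4, weeks to clearance were median 4 (range 2 to 9) for BCV and 9 (3 to 15) for SoC. Assumed: baseline mean 4.2 log10, noise SD 0.25, the shares not clearing, and risers gaining 0.5 to 2 log10 by Week 8. Four scenarios were kept because their SoC AAUC SD (0.97 to 1.05) matches 1.03:

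- A: 3/18 BCV and 15/23 SoC do not clear and stay flat; baseline SD 0.9.
- B: same shares, half of them rising; baseline SD 0.3.
- C: 25% in both arms do not clear, half rising; baseline SD 0.9.
- D: 50% in both arms do not clear and stay flat; baseline SD 0.9.

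The shares in A and B follow from the counts in Section 4.4 (15 of 18 and 8 of 23 with a resolution value), which may not include every clearer.

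Table 4 gives a document-based death timing. Of 69 pediatric subjects on study at Week 4, 4 + 4 + 7 + 9 = 24 died. Of 66 at Week 6, 5 + 2 + 7 + 7 = 21 died. So 3 of 24 deaths are placed in Weeks 4 to 6 and the rest in Weeks 6 to 16.

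| Assumed timing of deaths | Excess in non-survivors (log10) | Two-sided p < 0.05 |
|---|---|---|
| Weeks 0.5–16 | 0.28 to 0.37 | 18–48% |
| Weeks 4–16 | 0.15 to 0.21 | 7–17% |
| From Table 4 | 0.14 to 0.20 | 7–15% |
| Weeks 8–16 | 0.07 to 0.12 | 4–8% |

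The first row is an upper case: Section 4.3.2 sets out to exclude subjects unlikely to reach Week 4. If viremia rises in all subjects, the difference reverses (−0.14 to −0.38).

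Other assumed curves, not tuned to the SD of 1.03 and with exponential death times from randomization, gave 0.33 to 0.73 log10 and 20% to 100%. The documents therefore fix the sign, given falling viremia, but not the size.

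**The alternatives.** In the four matched scenarios, a Week 4 landmark, a Week 6 landmark and a Cox model with time-updated viremia each rejected in 4% to 6% of datasets.

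**The case for a change.** The case for a change is respectable. The gap is real, because no part of Section 12 gives a method for this objective. One of the sponsor's own displays is the vulnerable comparison. The death-related sensitivity analyses do not reach it. The trial is open label, which makes prespecification more useful. A sentence naming a landmark or time-updated analysis would cost nothing in data: AAUC at Weeks 4 and 6 is already an endpoint (Section 5.3.2), and sampling is weekly to Week 16.

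All of that stands as description. It does not show a stated rule that gives a wrong answer. The harm needs the analysts to choose one particular comparison out of three that the protocol displays, and it needs viremia to fall on average. Section 4.3.7 builds the surrogate argument on earlier trials, expanded access and the literature; nothing assigns that task to this trial's correlation.

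The alternatives also have costs. With 14 to 34 deaths after the landmark, 80% power at two-sided 5% needs a difference of about 2.8 × √(1/14 + 1/127) = 0.79 SD down to 2.8 × √(1/34 + 1/107) = 0.55 SD. They cover mortality only, whereas the objective concerns clinical outcome more widely. Landmark week, horizon and adjustment for arm are ordinary SAP choices.

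**Conclusion.** The arithmetic is right, but no change to the plan follows. This is missing detail on one secondary correlation, left to the SAP, and a statistician would ordinarily fill it with methods the protocol already displays.

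If the vulnerable comparison were used, the best-anchored estimate is a spurious excess of 0.14 to 0.20 log10 and a false-positive rate of 7% to 15% against 5%. That rests on assumed viral curves and on Table 4 timing. Table 4 states no mortality horizon and includes disseminated disease, so timing here may differ: earlier deaths would enlarge the effect, and deaths after Week 8 would bring it close to nominal.

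The point does not show that the associations in Section 4.3.7 are spurious. The primary, mortality and safety conclusions do not depend on this correlation. Whoever writes the SAP may reasonably treat any plot of death-truncated Week 16 AAUC by vital status as descriptive.

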7.1. Subject Inclusion Criteria

Subject must meet all of the following criteria, as applicable, to be eligible for participation in this study:

1. Aged at least 2 months and less than 18-years-old on Day 1
2. Have received a T cell-depleted allogeneic (i.e., non-autologous) HCT within the previous 100 days, where "T cell-depleted" describes EITHER:
 - ex vivo T cell depletion via positive selection (e.g., CD34+ cell) or negative selection (e.g., T cell receptor α/β or CD3+ cell removal by column filtration), OR
 - serotherapy with ATG (cumulative dose of ≥ 3 mg/kg rabbit-derived ATG or ≥ 50 mg/kg of equine-derived ATG) administered within 10 days prior to transplant or at any time post-transplant and prior to Day 1 OR
 - serotherapy with alemtuzumab administered within 30 days prior to transplant or at any time post-transplant and prior to Day 1

3. First detectable AdV DNA plasma viremia since the qualifying transplant occurred within 21 days prior to Day 1
4. AdV DNA plasma viremia ≥ 1000 copies/mL and rising, defined as two consecutive results ≥ 1000 copies/mL from the designated central virology laboratory, with the second result being greater than the first. The second sample must be drawn at least 48 hours after the first sample and no more than 7 days prior to Day 1
5. If male of reproductive potential, willing to use an acceptable contraceptive method(s) throughout the duration of his participation in the study and until 90 days following last dose of BCV when engaging in sexual intercourse with a female partner of childbearing potential
6. If female of child-bearing potential (i.e., post menarche and not surgically sterilized), willing to use two acceptable contraceptive methods, one of which must be a barrier method, throughout the duration of her participation in the study and until 90 days following last dose of BCV when engaging in sexual intercourse with a non-sterile male
7. Able to provide written informed consent or assent, with legal guardian consent, as required by applicable local or national law and institutional practice, based on the age of the subject
8. Available to participate in all required study activities for the entire duration of the study (i.e., inclusive of the Week 36 assessment)

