- Multiple imputation, where the missing part of the trajectory is imputed based on a model ([Rubin 1978](#)). This imputation is repeated to create multiple simulated data sets (e.g., 5-times the number of deaths plus drop-outs). Each of these simulated data sets is analyzed independently and the results from these analyses are pooled to yield a final inference.
- Undetectable imputation, where the missing part of the trajectory is imputed as undetectable.

In addition to the above, three other supportive analyses are proposed to directly account for subjects who die prior to Week 16:

- Baseline imputation, where the missing part of the trajectory for deaths only is imputed at the baseline value for the subject.
- Analysis of time below the detection limit, whereby subjects who die are considered to be above the detection limit after death. This approach will be repeated using time below 1000 copies/mL, which is a clinically-meaningful level of viremia often signaling viral control vs. need to address in clinical practice.
- Generalized pairwise comparisons of prioritized outcomes ([Buyse 2010](#)). In this approach, all BCV subjects are compared with all SoC subjects in the same stratum. Comparisons will be made based on the following hierarchy:
 - Alive or dead at Week 16
 - If both die before Week 16, compare time to death
 - If both are alive at Week 16, compare AAUC

Each comparison yields a favorable, unfavorable, or neutral result. The “proportion in favor of treatment” (Δ) is the net difference between the number of favorable pairs and the number of unfavorable pairs divided by the total number of pairs. The null hypothesis $H_0: \Delta=0$ is tested using a randomization test.

Another important factor that may influence the primary inference is the imputation of undetectable and BLQ AdV viremia values, with additional sensitivity analyses conducted in order to assess the potential impact of this imputation:

- Impute all undetectable/BLQ values at 1 copy/mL (i.e., 0 log₁₀ c/mL)
- Impute all undetectable/BLQ values at 189 copies/mL
- Impute all values < 1000 copies/mL at 1 copy/mL

In addition, a supportive analysis of overall mortality (adjusting for advanced baseline disease, [Matthes-Martin 2008](#)) will examine the non-inferiority of BCV treatment to SoC. No negative impact on mortality will be concluded if the upper bound of the one-sided 95% confidence

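### Two planned sensitivity analyses can score a death better than the primary analysis does, so they are not conservative if brincidofovir has more deaths on rising viremia

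*Combined protocol and SAP*

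**What the plan says.** Under Section 12.4.1, subjects who die or are lost before Week 16 are "accounted for inherently in the AAUC approach by truncating their follow-up period, thereby normalizing AUC over time of follow-up". The section expects that "approximately 16% to 24% of subjects are expected to die by Week 16" and that loss to follow-up will be nil or close to it. It then lists supportive analyses in two groups.

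- The first group covers deaths and drop-outs together: "The first three approaches are proposed to account for these subjects in a typical missing data framework". It holds jump to reference, multiple imputation, and this rule: "Undetectable imputation, where the missing part of the trajectory is imputed as undetectable".
- The second group is meant to deal directly with deaths before Week 16. Its first member is baseline imputation, where "the missing part of the trajectory for deaths only is imputed at the baseline value". The other two are time below the detection limit (repeated at 1000 copies/mL), which counts the dead as above the limit, and pairwise comparisons that rank survival and time to death ahead of AAUC.

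A mortality non-inferiority analysis follows. The section does not say in which direction baseline or undetectable imputation is expected to move the result.

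**The concern.** An analysis billed as accounting for death should be at least as hard on a death as the primary analysis is. Baseline imputation is not, if the virus was climbing. Section 7.1 admits subjects on two consecutive qualifying results, "with the second result being greater than the first", so viremia is rising at entry, and a subject whose treatment fails may well average above baseline before dying. Undetectable imputation gives a subject who died a cleared virus through Week 16.

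Excess deaths on BCV are not a remote possibility. Section 4.2.3.1 reports higher overall and non-relapse mortality on BCV in Study CMX001-301 (not statistically significant), and Section 4.3.7 includes the mortality comparison in order to rule out harm. If that pattern recurred, agreement between these two analyses and the primary could be read as robustness although both had moved the estimate towards BCV.

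**Working it through.** **Scale.** Section 12.1 gives SD 1.03 and a difference of 0.6; the synopsis gives 94 and 47 subjects. The standard error is 1.03 x sqrt(1/47 + 1/94) = 0.184, and 0.6/0.184 - 1.96 = 1.30, so power is 90.3% (89.9% with the noncentral t). The stated power of above 90% is reproduced under the normal approximation, assuming two-sided 0.05.

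**Formulas.** Let T be the week of death, M the mean log10 viremia up to death, B baseline and L the last value. Section 12.4.1 sets the value for undetectable: "AdV viremia values that are undetectable will be imputed at 99 copies/mL", which is 1.996 log10.

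- Primary: M
- Baseline imputation: [T x M + (16 - T) x B]/16, below the primary when M > B
- Undetectable imputation: [T x M + (16 - T) x 1.996]/16, below the primary when M > 1.996
- Higher of baseline and last: [T x M + (16 - T) x max(B, L)]/16

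**One death.** The documents give no trajectories, so these are assumed. For a linear rise from 4 to 6 with death at Week 6, M = 5.0:

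- baseline (30 + 40)/16 = 4.375
- undetectable (30 + 19.96)/16 = 3.12
- higher-of (30 + 60)/16 = 5.625

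| Assumed course (log10) | Primary | Baseline | Undetectable | Higher-of |
|---|---|---|---|---|
| 4 to 6, death Week 6 | 5.00 | 4.375 | 3.12 | 5.625 |
| 4, 5, 6, 6.5, 7, death Week 4 | 5.75 | 4.44 | 2.93 | 6.69 |
| Flat at 4, death Week 6 | 4.00 | 4.00 | 2.75 | 4.00 |
| 4, 3, 2.5, then undetectable from Week 3, death Week 8 | 2.31 | 3.15 | 2.15 | 3.15 |

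**Between arms.** If deaths in both arms follow the first course, the BCV-minus-SoC difference shifts by (BCV mortality - SoC mortality) x (imputed - primary). The per-death changes are -0.625, -1.88 and +0.625. Negative favours BCV.

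| BCV vs SoC mortality | Baseline | Undetectable | Higher-of |
|---|---|---|---|
| 24% vs 16% | -0.05 | -0.15 | +0.05 |
| 20% vs 20% | 0 | 0 | 0 |
| 14% vs 20% (planned range) | +0.04 | +0.11 | -0.04 |
| 21% vs 30% (planned range) | +0.06 | +0.17 | -0.06 |

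Against a standard error of 0.184, the first row is about 0.3 and 0.8 of a standard error for the two planned rules. A steeper assumed course (M = 6.0, baseline 4.0, death at Week 6) gives -0.10 and -0.20 at 24% vs 16%.

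**Simulation.** 300 trials per scenario used ANCOVA on baseline, deaths between Weeks 3 and 14, no virologic treatment effect given vital status, and 24% vs 16% mortality.

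| Course in subjects who die | Primary | Baseline | Undetectable |
|---|---|---|---|
| Rising 0.5 log10 per week | 0.281 | 0.219 | 0.145 |
| Flat | 0.126 | 0.127 | 0.048 |
| Falling 0.3 log10 per week | 0.046 | 0.079 | 0.004 |

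Baseline imputation moves towards BCV only when the virus was rising before death. Undetectable imputation moves towards BCV in all three.

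**Other analyses on the AAUC scale.** Jump to reference fills in the control average and multiple imputation a model prediction. Neither is specified to score a death as worse than the subject's own mean.

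**The case against.** The other side has real force, and most of it stands.

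- *Baseline imputation works both ways.* Truncation flatters a subject who clears virus and then dies; baseline imputation corrects that (2.31 to 3.15). Such deaths are not rare. In Table 4, among paediatric CMX001-304 subjects still on study at Week 4, 4 + 7 = 11 deaths were in those undetectable at Week 4 and 4 + 9 = 13 in the others. The table gives no cut-off, so some may fall after Week 16. Rising viremia at entry is also a pre-randomisation condition and does not establish the course before death.
- *The planned direction is the opposite.* Section 12.4.1 expects BCV mortality to be 6 to 9 points lower. Both rules then move against BCV and act as stress tests.
- *Death is penalised elsewhere.* The pairwise, time-below-limit and mortality analyses all count it as unfavourable. Undetectable imputation sits in the missing-data group, not among the analyses aimed at deaths.

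These points defeat a stronger reading that a reader might infer, namely that the two analyses cannot test whether deaths drive the result. They do not remove the narrower problem. The pairwise and time-below-limit analyses report a net proportion and a duration, so neither shows how far the log10 AAUC difference would move if deaths were scored as failures.

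**Conclusion.** The concern holds in a limited form. Neither baseline nor undetectable imputation is conservative if BCV has more deaths on rising viremia, and no planned analysis on the log10 AAUC scale reliably treats death as unfavourable. Under the assumed 4-to-6 course, an 8-point excess of BCV deaths moves the treatment difference by about -0.05 and -0.15. These sizes rest on the assumed trajectory, on deaths following the same course in both arms, and on the excess itself.

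A reader might instead take the change in one arm's mean with 20% such deaths (0.20 x -0.625 = -0.13 and 0.20 x -1.88 = -0.38) and set it beside 0.6. That comparison is not valid, because 0.6 is a between-arm difference; with equal deaths and equal courses the between-arm shift is zero. The primary analysis and its error rate are unaffected.

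**What to change.** In Section 12.4.1 and the SAP:

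1. For subjects who die, impute the missing part at the higher of baseline and last observed viremia through Week 16, in place of or beside the baseline rule. It matches the baseline rule for a responder who dies below baseline and stops crediting deaths on rising virus. A death after a mid-course peak can still score below its own mean. Placing it beside the baseline rule keeps the check that works against BCV when SoC has more deaths; the new rule then moves towards BCV (-0.04 to -0.06 above).
2. Keep undetectable imputation for all subjects. State that it lowers the AAUC of nearly every death and is not evidence of robustness if BCV mortality is higher. Restricting it to subjects lost alive would nearly empty it, since such losses are expected to be negligible.
3. Leave the pairwise, time-below-limit and mortality analyses unchanged.

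The cost is a sentence or two and one more supportive analysis on data already collected, slightly less favourable to the arm with more deaths. Section 12 allows SAP amendments until the database lock for the primary analysis. No power or sample-size figure changes.
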